- Symptomatic subjects: At least 14 days have passed since recovery, defined as resolution of fever without use of antipyretics and improvement in symptoms
- Asymptomatic subjects: At least 14 days have passed since the first positive molecular (i.e., PCR) test result.

Laboratory values can be re-tested once during the screening period. If the re-tested lab value(s) remain(s) exclusionary, the subject will be considered a screen failure. Redrawing samples if previous samples were unable to be analyzed would not count as a retest since previous result was never obtained.

Investigational Product:	Risankizumab
Doses:	Risankizumab 1800 mg IV Q4W Risankizumab 1200 mg IV Q4W Risankizumab 360 mg SC Q8W Risankizumab 180 mg SC Q8W
Mode of Administration:	Risankizumab solution for infusion (IV) Risankizumab solution for injection (SC)
Reference Therapy:	Placebo for Risankizumab
Dose:	Placebo: N/A
Mode of Administration:	Placebo solution for infusion (IV) Placebo solution for injection (SC)
Duration of Treatment:	12 to 24 weeks
The study will include a Screening period of approximately 35 days and a double blind induction period of 12 weeks. All subjects who do not achieve clinical response at Week 12 will be eligible to receive blinded risankizumab treatment over a subsequent 12 week period. There will be a follow up call 140 days from the last dose of study drug to obtain information on any new or ongoing AEs for those subjects who do not enroll into Study M16-066 or discontinue from the study prematurely.	
Criteria for Evaluation:	
Clinical Remission per Adapted Mayo: stool frequency subscore (SFS) ≤ 1 and not greater than baseline, rectal bleeding subscore (RBS) = 0, and endoscopic subscore ≤ 1 without the evidence of friabilityClinical Response per Adapted Mayo: decrease from Baseline ≥ 2 points and $\geq 30\%$, PLUS a decrease in RBS ≥ 1 or an absolute RBS ≤ 1

Criteria for Evaluation (Continued):

- **Clinical Response per Partial Adapted Mayo (without endoscopy):** decrease from Baseline ≥ 1 points and $\geq 30\%$, PLUS a decrease in RBS ≥ 1 or an absolute RBS ≤ 1
- **Clinical Remission per Full Mayo:** Full Mayo score ≤ 2 with no subscore > 1
- **Endoscopic Improvement:** endoscopy subscore of 0 or 1 without the evidence of friability
- **Endoscopic Remission:** endoscopic subscore = 0
- **Histologic Remission:** Geboes score of < 2.0
- **Histologic Endoscopic Mucosal Remission (HEMR):** Endoscopy subscore of 0 and Geboes score < 2.0
- **Histologic Endoscopic Mucosal Improvement (HEMI):** endoscopic subscore of 0 or 1 without the evidence of friability and Geboes score ≤ 3.1

Note: Evidence of friability during endoscopy in subjects with otherwise "mild" endoscopic activity will confer an endoscopic subscore of 2.

Efficacy (Risankizumab Versus Placebo): The primary endpoint is the same for Sub-Studies 1 and 2.

Primary Endpoint:

The achievement of clinical remission per Adapted Mayo score at Week 12.

Sub-Study 1 Secondary Endpoints:

1. The achievement of endoscopic improvement at Week 12
2. The achievement of clinical remission per Full Mayo score (defined as a Full Mayo score ≤ 2 with no subscore > 1) at Week 12 in subjects with a Full Mayo score of 6 to 12 at Baseline
3. The achievement of clinical response per Adapted Mayo score at Week 12
4. The achievement of clinical response per Partial Adapted Mayo score at Week 4
5. The achievement of endoscopic remission at Week 12
6. Occurrence of subjects with hospitalizations through Week 12
7. The achievement of HEMR at Week 12
8. Change from Baseline to Week 12 in UC-Symptom Questionnaire (UC-SQ)
9. Change from Baseline to Week 12 in Inflammatory Bowel Disease Questionnaire (IBDQ)
10. Change from Baseline to Week 12 in Short Form-36
11. Change from Baseline to Week 12 in Functional Assessment of Chronic Illness Therapy-Fatigue (FACIT-Fatigue)
12. UC-related surgeries through Week 12

Sub-Study 2 Secondary Endpoints:

1. The achievement of clinical response per Adapted Mayo score at Week 12
2. The achievement of endoscopic improvement at Week 12
3. The achievement of histologic endoscopic mucosal improvement (HEMI: Endoscopic subscore of 0 or 1 without evidence of friability and Geboes score ≤ 3.1) at Week 12
4. The achievement of endoscopic remission at Week 12
5. The achievement of clinical response per Partial Adapted Mayo score at Week 4
6. The achievement of no bowel urgency at Week 12

Criteria for Evaluation (Continued):**Sub-Study 2 Secondary Endpoints (Continued):**

7. The achievement of no abdominal pain at Week 12
8. The achievement of histologic endoscopic mucosal remission (HEMR: Endoscopy subscore of 0 and Geboes score < 2.0) at Week 12
9. Change from Baseline to Week 12 in Functional Assessment of Chronic Illness Therapy-Fatigue (FACIT-Fatigue)
10. Change from Baseline to Week 12 in Inflammatory Bowel Disease Questionnaire (IBDQ) total score
11. Occurrence of UC-related hospitalizations through Week 12
12. The achievement of no nocturnal bowel movements at Week 12
13. The achievement of no tenesmus at Week 12
14. Change from Baseline to Week 12 in number of fecal incontinence episodes per week
15. Change from Baseline to Week 12 in number of days per week with sleep interrupted due to UC symptoms.

Pharmacokinetics (PK):

Serum risankizumab concentrations will be determined from samples collected just prior to dosing at Weeks 4, 8, and 12/PD, and at Week 24 for subjects who undergo blinded risankizumab treatment during Induction Period 2.

Additionally, intensive pharmacokinetic assessment was performed in 24 subjects in Sub-Study 1 after the 3rd induction dose (Weeks 8 to 12). For Subjects who consented to the intensive pharmacokinetic assessment, in addition to the time points above, blood samples were collected at Week 8, immediately after completion of infusion and 2 hours post completion of infusion, and at Weeks 9, 10 and 11. Refer to Appendix H for more details. At the time of finalizing this amendment, intensive PK sub-study has been completed.

Immunogenicity:

Serum ADAs will be determined from samples collected just prior to dosing at Baseline and Weeks 4, 8, and 12/PD, and at Week 24 for subjects who undergo blinded risankizumab treatment during Induction Period 2.

Safety:

Incidence of adverse events (AEs), changes in vital signs, physical examination results, and clinical laboratory data will be assessed throughout the study.

Exploratory Research (Optional):

Prognostic, surrogate, predictive and pharmacodynamics biomarkers signatures may be investigated. Samples for different applications, potentially including but not limited to pharmacogenetic, epigenetic, transcriptomic, proteomic, metabolomic, metagenomic, phenotypic, functional and targeted investigations will be collected at various time points. Assessments may include but may not be limited to nucleic acids, proteins, metabolites, lipids, or peripheral blood mononuclear cells (PBMC).

Statistical Methods:**Sample Size Determination:****Sub-Study 1:**

For Sub-Study 1 (Phase 2b portion of the study), a total of 240 subjects were equally randomized with 1:1:1:1 ratio to three risankizumab treatment groups (600 mg, 1200 mg and 1800 mg IV Q4W) and the placebo group. Assuming clinical remission rate of 7% in the placebo arm and maximum of 25% in at least one of the risankizumab treatment groups at Week 12, a sample size of 60 subjects per treatment group is sufficient to test for the presence of a dose response signal with an average power of approximately 87% at 5% level of significance (one-sided), via modeling using Multiple comparison procedure and modeling (MCP-Mod) approach.

Sub-Study 2:

For Sub-Study 2, a total of 966 subjects will be allocated to risankizumab 1200 mg IV dose or placebo in a randomization ratio of 2:1. The sample size has been re-assessed after analyzing the combined PK, safety and efficacy results from Sub-Study 1. It is determined to provide adequate powers for the primary endpoint and selected ranked secondary endpoints and adequate responders to meet the sample size requirement for Study M16-066. Assuming clinical remission rate of 6% in the placebo arm and 16% of the risankizumab treatment arm at Week 12, a sample size of 644:322 subjects per arm will provide at least 90% power to detect the 10% treatment difference in the primary endpoint using two sided Miettinen and Nurminen test at a 0.05 significant level.

Analysis Sets:

For both Sub-Studies 1 and 2, efficacy analysis will be based on Intent-to-Treat (ITT) population and Safety analysis will be based on safety population. The ITT and safety populations for each sub-study are defined in the protocol Section 8.1.1. Subjects who received treatment in Induction Period 2 after Week 12 in both Sub-Study 1 and Sub-Study 2 will be analyzed separately for exploratory purpose.

Sub-Study 1:

The dose response modeling between risankizumab treatment groups and placebo on the primary efficacy endpoint clinical remission rate at Week 12 was performed using MCP-Mod approach in the ITT1A population.

The pairwise comparison between each risankizumab treatment group and placebo was performed using the 2-sided Cochran-Mantel-Haenszel (CMH) test and stratified by baseline corticosteroid use (yes vs no) and baseline Adapted Mayo score (≤ 7 vs > 7).

Non-responder imputation method (NRI) was used for the primary endpoint as the primary imputation method.

Continuous secondary efficacy endpoints were analyzed using a Mixed-Effect Model Repeated Measures (MMRM) method as the primary analysis.

Categorical secondary efficacy endpoints were analyzed using CMH controlling for stratification variables. NRI was used as the primary imputation method except for occurrence of hospitalization and UC-related surgeries, of which as observed data were used.

Sub-Study 2:

All efficacy comparisons between risankizumab and placebo will be based on corresponding ITT Population.

Statistical Methods (Continued):**Analysis Sets (Continued):**

The comparisons between [each] risankizumab treatment group and placebo for the primary efficacy endpoint clinical remission rate at Week 12 will be performed using 2-sided Cochran-Mantel-Haenszel (CMH) test and will be stratified by Advanced Therapy-IR status (yes vs no), baseline corticosteroid use (yes vs no), and baseline Adapted Mayo score (≤ 7 vs > 7). Non-responder imputation while incorporating multiple imputation to handle missing data due to COVID-19 or geo-political conflict in Ukraine and surrounding impacted regions (NRI-MI) will be used for the primary efficacy endpoint as the primary imputation method.

Continuous secondary efficacy variables will be analyzed using RTB-MI as defined in Section 8.1.2 with MMRM (for endpoints with more than one post-baseline visits) or with ANCOVA (for endpoints with one post-baseline visit) models.

Categorical secondary efficacy endpoints will be analyzed using CMH test controlling for stratification variables. NRI-MI will be used except for occurrence of UC-related hospitalization, of which AO data will be used.

Pharmacokinetics and Immunogenicity:

Serum risankizumab concentrations will be summarized at each time point for each dosing regimen using descriptive statistics. Population pharmacokinetic analyses combining the data from this study and other studies may be performed. Relationships between risankizumab exposures and efficacy and safety variables of interest may be explored.

ADA incidence will be summarized by cohort and study visits. ADA titers will be tabulated for each subject at the respective study visits. The effect of ADA on risankizumab pharmacokinetics, efficacy and/or safety variable(s) and/or any additional analyses will be explored.

Safety:

Treatment Emergent Adverse events (TEAEs), laboratory data and vital signs are the primary safety parameters in this study. All safety comparisons will be performed between treatment groups based on the corresponding safety population. TEAEs for each induction period are defined in protocol Section 8.1.7.

An overview of TEAEs, including TEAEs of special interest such as serious infection, malignancies, major adverse cardiovascular events, systemic hypersensitivity reactions/infusion reactions, TEAEs leading to death and TEAEs leading to premature discontinuation (see details in the SAP), TEAEs by Medical Dictionary for Drug Regulatory Activities (MedDRA version 18.1 or later) preferred term and system organ class, TEAEs by maximum relationship to study drug, and TEAEs by maximum severity will be summarized by number and percentage. Treatment group differences in the overall incidence of TEAEs will be assessed with Fisher's exact test for each preferred term.

Changes in laboratory data will be described using statistical characteristics and compared between-treatment groups will be performed using a one-way Analysis of Variance (ANOVA). In addition, shift tables and listings will be provided for abnormal values, whereby the normal range of the analyzing laboratory will be used. Vital signs will be analyzed similarly.

1.3**List of Abbreviations and Definition of Terms****Abbreviations**

6-MP	Mercaptopurine
AAC	Anaphylaxis Adjudication Committee
ADA	Anti-Drug Antibody
AE	Adverse Event
ALT	Alanine Transaminase
ANCOVA	Analysis of Covariance
ANOVA	Analysis of Variance
AST	Aspartate Transaminase
ANC	Absolute Neutrophil Count
AUC	Area under the plasma concentration-time curve
BID	Twice daily
BMI	Body Mass Index
BP	Blood pressure
BUN	Blood Urea Nitrogen
CAC	Cardiac Adjudication Committee
CD	Crohn's Disease
CDC	Centers for Disease Control and Prevention
CD4, CD8	Cluster of Differentiation
CGC	Common Gamma-Chain
CHF	Congestive Heart Failure
CI	Confidence Interval
C _{max}	Maximum Observed Plasma Concentration
CMH	Cochran-Mantel-Haenszel
COVID-19	Coronavirus Disease - 2019
CPK	Creatine Phosphokinase
CR	Clinical Remission
CRF	Case Report Form
CRP	C-Reactive Protein
C _{min}	Minimum Plasma Concentration During a Dosing Interval
CXR	Chest X-Ray
CYP3A	Cytochrome P450 3A

DMARD	Disease-Modifying Anti-Rheumatic Drug
DNA	Deoxyribonucleic Acid
ECG	Electrocardiogram
eCRF	Electronic Case Report Form
EDC	Electronic Data Capture
EIM	Extra-Intestinal Manifestations
Epro	Electronic Patient Reported Outcomes
EQ-5D	EuroQoL-5D
FACIT-F	Functional Assessment of Chronic Illness Therapy-Fatigue
FDA	US Food and Drug Administration
GCP	Good Clinical Practice
gp130	Glycoprotein 130
HBc Ab	Hepatitis B Core Antibody
HBs Ab	Hepatitis B Surface Antibody
HBs Ag	Hepatitis B Surface Antigen
HBV	Hepatitis B virus
HCV Ab	Hepatitis C Virus Antibody
HDL	High Density Lipoprotein
HIV	Human Immunodeficiency Virus
HRUQ	Health Resource Utilization Questionnaire
hsCRP	High-Sensitivity C-Reactive Protein
IBDQ	Inflammatory Bowel Disease Questionnaire
IC	Indeterminate Colitis
ICF	Informed Consent Form
ICH	International Conference on Harmonization
IEC	Independent Ethics Committee
IGRA	Interferon-Gamma Release Assay
IL	Interleukin
INR	International Normalized Ratio
IRB	Institutional Review Board
IRT	Interactive Response Technology
ITT	Intent-to-Treat
JAK	Janus Activated Kinase
LDL	Low Density Lipoprotein

LFT	Enter LFT definition
MedDRA	Medical Dictionary for Regulatory Activities
MMRM	Mixed Effect Repeated Measure
MTX	Methotrexate
NK	Natural Killer Cells
NOAEL	No Observable Adverse Effect Level
NRI	Non-Responder Imputation
NRI-MI	Non-Responder Imputation while incorporating multiple imputation to handle missing data due to COVID-19 or geo-political conflict in Ukraine and surrounding impacted regions
NSAID	Non-Steroidal Anti-Inflammatory Drug
NYHA	New York Heart Association
OC	Observed Cases
PD	Premature Discontinuation
PGIC	Patient Global Impression of Change
PGIS	Patient Global Impression of Severity
PE	Physical Examination
PG	Pharmacogenetic
PK	Pharmacokinetic
PPD	Purified Protein Derivative
QTc	QT Interval Corrected for Heart Rate
QTcF	QT Interval Corrected for Heart Rate by Fridericia's Formula
RA	Rheumatoid Arthritis
RAVE®	EDC System from Medidata
RBC	Red Blood Cell Count
RNA	Ribonucleic Acid
RBS	Rectal Bleeding Subscore
SAE	Serious Adverse Event
SAP	Statistical Analysis Plan
SDP	Study designated physician
SFS	Stool Frequency Subscore
STAT	Signal Transduction Activators of Transcription
TB	Tuberculosis
TEAE	Treatment-Emergent Adverse Event
T _{max}	Time to Maximum Observed Plasma Concentration

Risankizumab
M16-067 Protocol Amendment 4
EudraCT 2016-004677-40

TNF	Tumor Necrosis Factor
TPN	Total Parenteral Nutrition
Tyk2	Tyrosine Kinase 2
UC	Ulcerative Colitis
UCEIS	Ulcerative Colitis Endoscopic Index of Severity
ULN	Upper Limit of Normal
WBC	White Blood cell Count
WPAI	Work Productivity and Impairment Questionnaire

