This Phase 2b/3 study has an operationally seamless design and comprises two sub-studies. The purpose of this design is to seamlessly transition from the Phase 2b induction study to the Phase 3 induction study without enrollment pause. Sub-Study 1 was designed as a Phase 2b dose finding study to evaluate the efficacy, safety, and PK of risankizumab as induction treatment to identify the appropriate induction dose of risankizumab for further evaluation in Sub-Study 2. Sub-Study 2 is a Phase 3 induction study to evaluate the efficacy and safety of risankizumab versus placebo.

Sub-Study 1 (Phase 2b Induction):Induction Period 1:

Subjects (n = 240) who met all of the inclusion criteria and none of the exclusion criteria were randomized into the study in a 1:1:1:1 ratio to one of the following treatment groups:

- Group 1: Risankizumab 1800 mg IV Weeks 0, 4, 8 (n = 60)
- Group 2: Risankizumab 1200 mg IV Weeks, 0, 4, 8 (n = 60)
- Group 3: Risankizumab 600 mg IV Weeks 0, 4, 8 (n = 60)
- Group 4: Placebo IV Weeks 0, 4, 8 (n = 60)

The randomization at baseline was stratified by baseline steroid use (yes vs no) and baseline Adapted Mayo score (≤ 7 vs > 7). Endoscopy and evaluation of clinical response and remission will occur at Week 12.

Subjects in Sub-Study 1 who achieved clinical response per Adapted Mayo score (locally read Mayo endoscopic subscore) after completion of the 12-week Induction Period 1 were eligible to be enrolled into maintenance Study M16-066. Clinical response is defined as a decrease from baseline in the Adapted Mayo score ≥ 2 points and $\geq 30\%$ from baseline, PLUS a decrease in rectal bleeding subscore (RBS) ≥ 1 or an absolute RBS ≤ 1 . Subjects who did not achieve clinical response at Week 12 were eligible to receive blinded risankizumab treatment in Induction Period 2 as specified below. Subjects were not eligible to enter Induction Period 2 until the Week 12 endoscopy has been completed.

Methodology (Continued):**Sub-Study 1 (Phase 2b Induction) (Continued):**Induction Period 2:

At Week 12, subjects who did not achieve clinical response were be randomized by Interactive Response Technologies (IRT) to Induction Period 2, a double-blind, double-dummy 12-week treatment period to evaluate reinduction with risankizumab versus starting maintenance dosing on clinical response status.

Subjects who received IV risankizumab induction were randomized 1:1:1 to:

- Group 1: 1800 mg IV risankizumab Weeks 12, 16, 20

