- Group 2: 360 mg SC risankizumab Weeks 12, 20
- Group 3: 180 mg SC risankizumab Weeks 12, 20

The randomization in Period 2 was stratified by baseline steroid use (yes vs no) and baseline Adapted Mayo score (≤ 7 vs > 7).

Subjects who received IV placebo induction treatment received:

- Group 4: 1800 mg IV risankizumab Weeks 12, 16, 20

Subjects randomized in Groups 1 and 4 received placebo SC and subjects randomized in Groups 2 and 3 received placebo IV, in order to keep the blind. The IV risankizumab dose or matching IV placebo were given at Weeks 12, 16, and 20. The SC risankizumab dose or matching SC placebo were given at Weeks 12, and 20. At Week 24, subjects who received blinded risankizumab treatment during Induction Period 2 were reassessed and underwent a third endoscopy for evaluation of mucosal inflammation.

Subjects who achieved clinical response per Adapted Mayo score (locally read Mayo endoscopic subscore) at Week 24 were eligible to enter into the maintenance Study M16-066. Subjects without clinical response at Week 24, as well as all subjects who terminated the study early (including subjects who were eligible for but did not receive blinded risankizumab therapy during Induction Period 2), were discontinued and have a follow-up call 140 days from the last dose of study drug to obtain information on any new or ongoing AEs.

Dose Selection Analysis:

After 240 subjects were randomized and completed the 12-week Induction Period 1, dose response and exposure response analysis for the key efficacy and safety variables were performed. Based on this analysis, one induction dose of risankizumab has been identified (risankizumab selected dose) for evaluation in Sub-Study 2 (Phase 3 Induction). The results of this analysis were reviewed and discussed with regulatory authorities, as applicable, prior to initiation of enrollment of subjects in Sub-Study 2.

During the analysis period, additional subjects continued to be enrolled in the 1800 mg dosing group, on an open-label basis, to avoid interrupting the study activities during the analysis period and to generate a sufficient number of subjects with clinical response to be enrolled into the maintenance Study M16-066. The data collected from these additional subjects will not be included in the primary analysis but reported in the clinical study report.

Methodology (Continued):**Sub-Study 2 (Phase 3 Induction):**Induction Period 1:

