Subjects taking oral corticosteroids at Baseline must continue their concomitant treatment at the Baseline dose for the duration of Induction Period 1. Initiation and/or increasing doses of systemic and/or UC-related corticosteroids after Baseline is prohibited. Decreasing doses of oral corticosteroids is prohibited during Induction Period 1, except in the event of moderate-to-severe treatment related toxicities in the opinion of the investigator.

Methodology (Continued):

Subjects who enter Induction Period 2 will be allowed to taper their oral corticosteroids at the discretion of the Investigator. While stopping the taper is permitted, increasing doses above the Baseline dose is prohibited.

Dose Selection:

Sub-Study 2 (Phase 3 induction study) will evaluate IV risankizumab 1200 mg during induction. The selection of doses was informed by the analysis of safety and efficacy data, as well as the dose-response and exposure-response relationships of efficacy from Sub-Study 1 (Phase 2b dose finding study).

Induction Period 2 will evaluate IV (1800 mg [Sub-Study 1] or 1200 mg [Sub-Study 2] Q4W) or SC (180 mg or 360 mg Q8W; maintenance dosing regimen) risankizumab. The purpose of Induction Period 2 is to evaluate the efficacy and safety of re-induction of risankizumab versus starting maintenance regimen on clinical response status. Data from the Phase 2 study in subjects with CD suggested that re-induction with 600 mg IV increased both clinical response and clinical remission in subjects with inadequate response at Week 12. The selection of the SC doses is based on safety and efficacy data, as well as the exposure-response relationship, of the maintenance period during the Phase 2 study in subjects with CD that evaluated 180 mg SC risankizumab for maintenance. A higher dose of 360 mg Q8W is proposed to provide exposures reasonably separated with 180 mg Q8w dose to characterize the exposure-response relationship during maintenance phase with a potential of 360 mg Q8w dose to maintain higher response compared to 180 mg Q8w dose.

Data Monitoring Committee (DMC):

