At the time of this amendment, dose selection enrollment has been closed, 340 subjects were enrolled and received risankizumab 1800 mg IV and all subjects have completed the 12-week double-blind, placebo-controlled induction period.

Subjects follow the same study design described for Sub-Study 1 above (i.e., study visits and subject flow through Induction Period 1 and Induction Period 2). In addition, for subjects where endoscopy cannot be performed at Week 12 or Week 24 due to COVID-19 pandemic restrictions or geo-political conflict in Ukraine and surrounding impacted regions, clinical response will be calculated using Partial Adapted Mayo score (decrease from baseline in the Partial Adapted Mayo score ≥ 1 points and $\geq 30\%$ from baseline, PLUS a decrease in rectal bleeding subscore (RBS) ≥ 1 or an absolute RBS ≤ 1). Subjects who have missing endoscopy due to COVID-19 or geo-political conflict in Ukraine and surrounding impacted regions and achieve clinical response per Partial Adapted Mayo score will be eligible for Study M16-066 Sub-Study 3.

Sub-Study 2: Phase 3 Induction

Sub-Study 2 Induction Period 1:

Once the dose selection analysis in Sub-Study 1 is completed, subjects (n = 966) who meet all of the inclusion criteria and none of the exclusion criteria will be enrolled into the double-blind 12-week study and randomized in a 2:1 ratio to one of the following treatment groups (Figure 3):

- Group 1: Risankizumab 1200 mg Weeks 0, 4, 8 (n = 644)
- Group 2: Placebo IV Weeks 0, 4, 8 (n = 322)

Sub-Study 2 will enroll approximately 541 bio-IR subjects.

The randomization at Baseline will be stratified by number of prior failed biologics (0, 1 vs > 1), baseline steroid use (yes vs no), and baseline Adapted Mayo score (≤ 7 vs > 7). Endoscopy and efficacy evaluation will occur at Week 12.

[figure not shown]
Subjects in Sub-Study 2 who achieve clinical response per Adapted Mayo score (locally read Mayo endoscopic subscore) after completion of the 12-week Induction Period 1 will be enrolled into maintenance Study M16-066. Subjects who do not achieve clinical response at Week 12, may be eligible to enter a blinded risankizumab treatment in Induction Period 2 as specified below.

Subjects are not eligible to enter Induction Period 2 until the Week 12 endoscopy has been completed, except in case of COVID-19 pandemic restrictions or geo-political conflict in Ukraine and surrounding impacted regions.

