8.0 Efficacy Analyses

8.1 General Considerations

The primary and secondary efficacy endpoints will be analyzed based on ITT1A in Induction Period 1 of Sub-Study 1 as the primary analysis.

The primary and ranked secondary efficacy endpoints will be analyzed based on ITT1B in Induction Period 1 of Sub-study 1 as the exploratory analysis.

All analyses for the efficacy endpoints in Induction Period 2 will also be performed based on ITT1_P2 for Sub-Study 1 for exploratory purpose.

For all efficacy endpoints, the descriptive statistics will be provided by treatment group for each induction period in each sub-study. The statistics include number of observations, mean, standard deviation, minimum, median, and maximum for continuous variables; and number and percentage of subjects for categorical variables.

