8.4 Secondary Efficacy Analyses

Sub-Study 1 – Induction Period 1:

For Induction Period 1 in Sub-Study 1, the ranked secondary and non-ranked secondary efficacy variables listed in Section 3.2 will be analyzed by treatment group for ITT1A as the primary analysis at the nominal α level of 0.05 (one-sided).

Continuous secondary efficacy variables will be analyzed using a Mixed-Effect Model Repeated Measures (MMRM) method. It will be used for primary inference purpose. Analysis of Covariance (ANCOVA) model using LOCF imputation method will be applied as sensitivity analysis.

Categorical secondary efficacy variables will be analyzed using the CMH test controlling for stratification variables. NRI imputation will be used for primary inference purpose and observed case analyses will be used for sensitivity analysis.

Additional exploratory analysis based on ITT1B will be provided for all ranked secondary efficacy variables: continuous secondary efficacy variables will be analyzed using MMRM method and descriptive statistics will be provided for categorical secondary efficacy variables with NRI imputation method.

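### Sub-Study 1 Period 2 is not reported by Period 1 dose, so its exploratory 1800 mg IV results mix same-dose re-induction with a higher IV dose after a lower one

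*Protocol*

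**What the plan says.** **Design.** Protocol sections 1.2 and 5.1 put 60 subjects on each of 600, 1200 and 1800 mg IV in Period 1, and 60 on placebo. Section 5.1 adds that "340 subjects were enrolled and received risankizumab 1800 mg IV" on an open-label basis and that they follow the same flow through both periods. Active non-responders at Week 12 are randomised 1:1:1 to 1800 mg IV, 360 mg SC or 180 mg SC, whatever IV dose they had before. Placebo non-responders all receive 1800 mg IV. On strata, the synopsis says "The randomization in Period 2 was stratified by baseline steroid use (yes vs no) and baseline Adapted Mayo score". Sections 5.1, 5.5.3 and 8.3 agree.

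**Purpose.** The synopsis gives the aim of Period 2 as "to evaluate the efficacy and safety of re-induction of risankizumab versus starting maintenance regimen". Section 5.6.4 repeats it.

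**Analysis.** Sub-Study 1 SAP 8.1 says "All analyses for the efficacy endpoints in Induction Period 2 will also be performed based on ITT1_P2 for Sub-Study 1 for exploratory purpose", with descriptive statistics by treatment group within each period. SAP 8.5 and 12.0 allow nominal two-sided 0.05 testing without multiplicity control. Protocol 8.1.6.2 plans a descriptive summary. The MMRM in SAP 8.2 carries the randomisation strata and the baseline value. The subgroup list in 8.6 omits Period 1 dose. Section 9.2.1 has three Period 2 safety labels, one per regimen.

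**Contrast.** Sub-Study 2 SAP 9.5.2 reports ITT2_P2 by treatment sequence. That sub-study has one active Period 1 dose, and its Period 2 IV dose equals it.

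**The concern.** The stated question contrasts another IV course with starting the SC maintenance regimen. In Sub-Study 1 the IV arm is a repeat of the same dose only for subjects who had 1800 mg in Period 1. For the others it is 1800/600 = 3 times or 1800/1200 = 1.5 times the dose they had failed to respond to.

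Protocol 5.6.4 gives a reason to keep these apart. Exposure-response modelling predicted better efficacy at higher exposure, with 1200 and 1800 mg both expected to outperform 600 mg. A non-responder to 600 mg and a non-responder to 1800 mg may therefore differ in what a further 1800 mg course can add.

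At stake is how the 1800 mg IV column is read: a reader who takes it as the effect of repeating induction would be reading a mixture. Under 9.2.1 the safety column may also absorb placebo non-responders having their first induction, because they have no label of their own.

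**Working it through.** The documents give no sample size, power or target difference for Period 2, so there is no planned figure to reproduce. The check concerns the make-up of the pool.

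**Inputs from the documents:** 60, 60 and 60 randomised to 600, 1200 and 1800 mg; 340 open-label at 1800 mg; 60 on placebo; 1:1:1 allocation of active non-responders.

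**Assumptions:** Week 12 non-response by dose is not given, so a range is used. Open-label subjects are taken to have the blinded 1800 mg rate, and all non-responders are taken to enter Period 2.

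**Step 1, lower-dose share of active entrants.** Let r600, r1200 and r1800 be the non-response rates.

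Share = (60·r600 + 60·r1200) / (60·r600 + 60·r1200 + 400·r1800).

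For the randomised cohort alone, replace 400 by 60.

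| Non-response 600/1200/1800 | Active entrants | Lower-dose share, all | Lower-dose share, randomised only |
|---|---|---|---|
| 50/50/50% | 260 | 60/260 = 23% | 60/90 = 67% |
| 60/50/40% | 226 | 66/226 = 29% | 66/90 = 73% |
| 80/60/40% | 244 | 84/244 = 34% | 84/108 = 78% |
| 40/50/60% | 294 | 54/294 = 18% | 54/90 = 60% |

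With any equal rate the shares are 120/520 = 23% and 120/180 = 67%.

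**Step 2, chance imbalance.** At 50% non-response there are 260/3 ≈ 87 per arm. Without stratification on Period 1 dose, the difference in lower-dose share between two arms has SD = √(2 × 0.23 × 0.77 / 87) = 0.064, about 6 points. A permutation check put the 95th percentile of the absolute difference at about 13 points. In the randomised cohort alone (30 per arm) it was about 23 points.

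**Step 3, what a pooled contrast would estimate.** Let w be the lower-dose share, e0 the IV-minus-SC effect after 1800 mg and e1 the effect after a lower dose. The pooled effect is (1 − w)·e0 + w·e1, which differs from e0 by w·(e1 − e0). Step 1 bounds w at about 0.18–0.34. The documents give neither e0 nor e1, and the difference is zero if they are equal. Stratifying or adjusting by Period 1 dose does not remove this term, because it still averages the dose-specific effects.

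**Step 4, placebo entrants in the safety label.** At 60% placebo and 50% active non-response (both assumed), 60 × 0.6 = 36 placebo and 520 × 0.5/3 = 86.7 active subjects receive 1800 mg IV, and 36/122.7 = 29%. At 70% and 40%, 42/(42 + 69.3) = 38%.

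**The case against.** The case against is substantial, and most of it limits the point rather than removing it.

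- **Bias.** A reader might infer that the IV and SC arms are confounded by Period 1 dose. They are not. The pooled non-responders are randomised, so the regimens are compared without systematic bias in that population, and ordinary standard errors already allow for chance imbalance.
- **A planned test.** A reader might take "Categorical secondary efficacy variables will be analyzed using the CMH test controlling for stratification variables" in Sub-Study 1 SAP 8.4 as the Period 2 analysis. That passage sits under the Induction Period 1 heading and its primary set is ITT1A. No CMH test on ITT1_P2 and no IV-minus-SC contrast is written. The pairwise log-rank and Cox comparison in 8.5 is against placebo, which Period 2 does not have as an arm. The nominal alpha permits testing without defining it.
- **Definition.** The documents do not define re-induction as repeating the same dose, and they state openly that the Sub-Study 1 IV dose is 1800 mg. Calling the move from 600 to 1800 mg something other than re-induction would impose an outside definition.
- **Prognosis.** The exposure-response text concerns Week 12 outcome. Nothing shows that Period 1 dose predicts Week 24 outcome among Week 12 non-responders, and section 5.6.4 calls the 1200-to-1800 mg increment modest.
- **Relevance.** Period 2 is exploratory and feeds neither the primary nor the dose-selection inference. Sub-Study 1 is closed, and Sub-Study 2 asks the question with a single active induction dose.

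What survives is narrower. Descriptive results by Period 2 treatment group carry the mixture whether or not a test is run, and the Sub-Study 1 SAP has no display that separates its parts.

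**Conclusion.** The point holds as a minor matter of reporting and interpretation. Period 1 dose is absent from the Period 2 strata and from every Period 2 display in the Sub-Study 1 SAP, so the 1800 mg IV results mix two kinds of subject. The lower-dose part is about 23% of active entrants with equal non-response and about 18–34% over the assumed rates. It is 60–78% if only the randomised cohort is counted. These shares rest on the stated arm sizes and on assumed non-response.

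A reader might go on to infer that re-induction is overstated by some number of points. The documents do not support any such number, because the effects by Period 1 dose are unknown and may be equal. No primary, ranked or dose-selection conclusion is affected.

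**What to change.** In Sub-Study 1 SAP 8.5 (efficacy) and 9.2.1 (safety labels), or in the clinical study report and marked as post hoc:

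- Report ITT1_P2 and SAS1_P2 by treatment sequence, Period 1 dose to Period 2 regimen, following Sub-Study 2 SAP 9.5.2.
- Show 1800-to-1800 mg IV against 1800-to-SC as one subset, and entrants from 600 or 1200 mg separately.
- Give placebo-to-1800 mg IV subjects their own label.
- If any nominal Period 2 test is run, include Period 1 dose (600, 1200, 1800 mg) as a covariate. Its role is precision and chance imbalance. It does not isolate same-dose re-induction; only the separate subset does that.

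**Cost.** No new data are needed, only SAP or report wording and extra table rows. Cells become small: at 50% non-response each lower dose supplies 60 × 0.5/3 = 10 subjects per Period 2 arm. The same-dose estimate rests on about three quarters of active entrants (400/520 = 77% with equal non-response). The results remain exploratory. No dose, allocation or clinical rule changes.
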